* We recognize that the actual home caregivers of young patients with asthma may be biologic parents, adoptive parents, foster parents, and other relatives and legal guardians. For simplicity, we will use the term "parents" to refer to all potential home caregivers and to distinguish the group from clinicians and other school and community-based caregivers.

community-based clinicians and service providers, as well as national experts in asthma and stress management.

Specific Aim 2. To determine the effect that a stress management intervention has on the primary measured outcome: symptom free days. Other patient/family-centered outcomes will include parent stress, quality of life, asthma morbidity, healthcare utilization, and medication adherence.

Hypothesis 1: The principal hypothesis is that the number of symptom-free days over a two week period (primary outcome) at 6 month follow-up will be significantly higher among parents in Arm 2 (usual care plus the intervention) than in Arm 1 (usual care alone).

[figure not shown]
Impact of Study on Health Decisions: The proposed study will provide novel insights into the contribution of parent stress to family difficulties in child asthma management and control. The primary goal of this project is to address the need for a multi-dimensional approach to a multi-faceted problem in asthma care and address disparities facing families, particularly in the area of stress management. This knowledge will inform the decisions of parents, in addition to health systems, clinicians, and community-based programs that seek to improve pediatric asthma outcomes and reduce disparities. Results of the study will be disseminated to a broad range of stakeholders, including parents of children with asthma, clinicians, and other service providers. The dissemination strategy will be developed in partnership with representatives of these key stakeholders.

B. BACKGROUND AND SIGNIFICANCE

Background: Burden of Pediatric Asthma on the Health of Children

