To address aim 2: To determine the effect that the stress management intervention has on the primary measured outcome: symptom free days. Other patient/family-centered outcomes will include parent stress, quality of life, asthma morbidity, healthcare utilization, and medication adherence. Baseline demographic characteristics will first be compared in univariate fashion between the two groups using the chi-squared test for categorical variables and the t-test for continuous variables. If any variable is not balanced by randomization, it will be used as a covariate in all secondary analyses. To test the hypothesis that the time average of number of symptom-free days over a two week period (primary outcome) at 3 and 6 month follow-up will be significantly higher among parents in Arm 2 (intervention) than in Arm 1 (usual care), a two sample t-test will be used to compare difference of mean symptom-free days over a two week period between the two arms with point estimates, 95% CI and p values being reported. Depending on the degree of dispersion, we may need to employ a Poisson or negative binomial model.

In secondary analysis, we will further explore the effect of the intervention by fitting random effect mixed models that (1) adjust for baseline covariates of interest, considered *a priori* or that differ between groups at baseline and are relevant to change in symptom-free days; (2) test for interaction between treatment effects and other covariates; and (3) examine patients who complete intervention and follow-up (per protocol analysis).

For continuous secondary outcomes, we will use the same approach as described above. For the categorical secondary outcomes, we will use the chi square test of whether relative rates between groups differ from 1. All subsequent estimates of relative rates (RR) will be adjusted (at the minimum) for age, sex, race/ethnicity and other covariates using generalized estimating equations (GEE). All estimates of RR will be reported with 95% confidence intervals (CIs). For measures of healthcare

utilization, the analysis will compare adjusted rates and RRs at 3 and 6 follow up. Depending on the degree of dispersion in the rates, these models will be based on either Poisson or negative binomial regression models.

Sensitivity analyses will be conducted to account for missing data. These will estimate the highest and lowest potential treatment effect for primary and secondary outcomes.

Missing Data

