Clinical research staff will be trained in the importance of completing all data fields. Based on our prior studies, we anticipate a rate of missing data for the primary outcome of <5%. All efforts will be made to minimize patient dropout. Frequent data queries will allow us to track missing data and retrain staff as needed. Sensitivity analyses will be conducted as described above. Reasons for participant drop out will be collected and reported. In cases of missing data, we will use multiple imputation (MI) to impute the missing values.

Sample Size Considerations: Power Analysis

This study is designed to detect the smallest clinically significant difference in mean symptom free days (SFD) between the intervention and control groups.

The initial sample size calculation was based on previous data from other studies, the improvements of 0.9-1.0 SFD per 14 days are feasible, the standard deviation of SFD is 2.7, and the within subject correlation is 0.3. Power analysis was calculated for the intervention effect on SFD while justifying two assessments for each subject. The table shows the total sample size needed to detect differences in SFD from 0.9 to 1.0 with different within subject correlation. The sample size of 152 is needed to detect the difference of 1.0 SFD with standard deviation of SFD of 2.7, within subject correlation of 0.3, power of 0.8 at alpha level of 0.05. With anticipation of attrition rate of 10%, we initially planned to enroll 168 children.

The sample size was recalculated on September 14, 2015, based on the baseline data collected from the first 60 participants, which showed the following: mean was 10.25 days, median was 11.5 days, standard deviation was 4.12. The sample distribution is not normal and approximated a Poisson distribution. Based on this distribution, the calculated sample size is 188, as can achieve 80% power at a 0.05 significance level to detect a response rate ratio of 1.15 with baseline response rate 0.8. Therefore, with 10% percent attrition rate, we now plan to enroll 207 participants.

| Power Calculation with Standard Deviation of 2.7, Power of 0.8, Alpha level of 0.5 | | | |
|---|--------------------|------------|-------------------------------|
| Difference | Correlation | N | N (with 10% attrition) |
| 0.9 | 0.1 | 158 | 174 |
| 0.9 | 0.15 | 166 | 183 |
| 0.9 | 0.2 | 172 | 190 |
| 0.9 | 0.25 | 180 | 198 |
| 0.9 | 0.3 | 186 | 205 |
| 0.9 | 0.35 | 194 | 214 |
| 0.9 | 0.4 | 200 | 220 |

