The sample distribution is not normal and approximated a Poisson distribution. Based on this distribution, the calculated sample size is 188 to achieve 80% power at a 0.05 significance level to detect a response rate ratio of 1.15 with baseline response rate of 10.25. Therefore, with 10% percent attrition rate, we planned to enroll 207 participants.

The primary analyses for this study will be conducted at 6m FU, and the same analyses will be completed with the 12m FU data.

The primary analysis for this study will be by intention to treat.

A per-protocol analysis will also be conducted. Per protocol will be defined as completion of all four one-on-one sessions.

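### The recalculated sample size of 188 does not follow from either stated baseline rate by the stated Poisson method, so the 80% power is not supported as written

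*Protocol*

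**What the plan says.** Protocol D.10 (Sample Size Considerations) first gives a calculation based on differences of 0.9 to 1.0 symptom-free days, SD 2.7, two assessments per child and a within-subject correlation of 0.3. It leads to 152 children.

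That calculation was replaced in September 2015 using baseline data from the first 60 participants: "mean was 10.25 days, median was 11.5 days, standard deviation was 4.12". The protocol adds: "The sample distribution is not normal and approximated a Poisson distribution". From this it derives 188, described as giving "80% power at a 0.05 significance level to detect a response rate ratio of 1.15 with baseline response rate 0.8", and 207 to be enrolled after allowing for attrition.

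The SAP (Sample Size Calculation) repeats the same data, N, power and ratio, but says the trial can "detect a response rate ratio of 1.15 with baseline response rate of 10.25".

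On the primary analysis, Protocol D.10 (aim 2) says that "a two sample t-test will be used to compare difference of mean symptom-free days", and adds: "Depending on the degree of dispersion, we may need to employ a Poisson or negative binomial model". The outcome there is the "time average of number of symptom-free days over a two week period (primary outcome) at 3 and 6 month follow-up". Hypothesis 1 in Protocol section A instead concerns "the number of symptom-free days over a two week period (primary outcome) at 6 month follow-up will be significantly higher", and the SAP also places the primary analysis at six-month follow-up. All tests are two-sided at 0.05 (D.10, General Considerations).

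**The concern.** Two documents attach different baseline rates to one result, and the protocol's 0.8 has neither a unit nor an exposure period. If the rate is unknown, so is the difference in days that the trial was sized to detect.

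The distribution named as the basis of the calculation does not resemble the summary statistics quoted just before it. The recalculation also drops the two assessments and the correlation that the initial one stated, and power depends strongly on whether one visit or the mean of two is analysed.

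Readers who use the design claim to judge what the trial could detect cannot verify it, and cannot tell whether it belongs to the planned primary test.

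**Working it through.** **Inputs.** N 188, read as a total because 207 are to be enrolled in all; ratio 1.15; power 80%; two-sided 0.05; mean 10.25, median 11.5, SD 4.12 (all D.10 and SAP). The outcome is a count of days out of 14 (D.6). Allocation is not stated, so 1:1 is assumed. (1.96 + 0.8416)² = 7.849; ln 1.15 = 0.13976, squared 0.019533.

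**1. Initial calculation.** Total N = 4 × 7.849 × 2.7² × (1 + 0.3)/2 ÷ 1.0² = 148.8, or 150 with equal arms. The protocol has 152, so this one essentially reproduces.

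**2. Recalculation by Poisson**, control count L per 14 days:
- Wald: N = 2 × 7.849 × (1/L + 1/(1.15L)) ÷ 0.019533
- Poisson regression: N = (1.96 × √4 + 0.8416 × √(2 + 2/1.15))² ÷ (0.019533 × L)

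| Reading of the baseline rate | L | Wald | Regression |
|---|---|---|---|
| SAP | 10.25 | 146.6 | 153.7 |
| 0.8 per day × 14 | 11.2 | 134.1 | 140.7 |
| 0.8 per 14 days | 0.8 | 1,878.1 | 1,969.3 |

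The quoted mean of 10.25 days rules out the last row. None gives 188.

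**3. Poisson power at 188.** For L = 10.25, SE = √[(1/10.25 + 1/11.7875)/94] = 0.04405. Then 0.13976/0.04405 − 1.96 = 1.21, which is 89%. For L = 11.2 it is 91%.

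**4. What would give 188.**
- A Poisson control count of 146.6 × 10.25/188 = 7.99 (Wald) or 153.7 × 10.25/188 = 8.38 (regression).
- L = 11.2 with 90% power instead of 80% (187.1).
- A two-means formula with 11.2 days, difference 0.15 × 11.2 = 1.68 and SD 4.12: 4 × 7.849 × 16.97/1.68² = 188.8. With 10.25 days (difference 1.5375) the same formula gives 225.4.

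Each needs an input or a method that the documents do not state.

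**5. Fit to a Poisson.** Variance 4.12² = 16.97; 16.97/10.25 = 1.66, where a Poisson has 1. A Poisson with mean 10.25 has median 10 (observed 11.5) and puts 9.7% of its probability above 14, which this outcome cannot reach.

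**6. Power at 188 for a control mean of 10.25** (difference 1.5375 days, 94 per arm, noncentral t):
- Month 6, SD 4.12 in both arms: SE = 4.12 × √(2/94) = 0.601; 1.5375/0.601 = 2.56; power 72%.
- Mean of months 3 and 6: SD = 4.12 × √((1 + 0.3)/2) = 3.32; power 88%. The correlation of 0.3 is carried over from the initial calculation. Over the range of the protocol's table, 0.1 to 0.4, power is 93% to 86%.
- Variance shrinking towards the ceiling in proportion to m(14 − m): the factor is 16.97/(10.25 × 3.75) = 0.4416, so the intervention variance is 0.4416 × 11.7875 × 2.2125 = 11.52. The average variance is 14.25 (SD 3.77). Power is 79% at month 6, or 93% for the mean with correlation 0.3.
- Count model with observed dispersion, month 6: SE = 0.04405 × √1.656 = 0.0567; 0.13976/0.0567 − 1.96 = 0.51; power 69%. The total needed for 80% is 243-255.

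**7. The 11.2-day reading.** The intervention mean would be 11.2 × 1.15 = 12.88. On a 0-14 scale the SD cannot exceed √(12.88 × 1.12) = 3.80, so powers computed with SD 4.12 in that arm are not attainable. None is given here.

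**The case against.** The strongest reply is that 188 is adequate or better under the method the documents name: Poisson power is 89% at 10.25 and 91% at 11.2. That is correct, and it counts against reading the discrepancy as a shortfall. It does not rescue the statement that 188 is the N for 80%, and it relies on the distribution that the quoted data contradict.

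A second reply is that 188 can be recovered, most neatly by the two-means formula with 11.2 days and SD 4.12. But that is not a Poisson calculation, the daily unit is inferred, 188.8 rounds up past 188, and it disagrees with the SAP's 10.25. With several routes available, no single one can be taken as the sponsor's.

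Third, D.10 allows a Poisson or negative binomial model, so sizing on a rate ratio is not foreign to the plan. This stands. D.10 makes that choice depend on dispersion, however, and the calculation makes no allowance for it.

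Fourth, holding the SD at 4.12 is pessimistic for a bounded outcome. This also stands, which is why the 72% and 69% are shown beside the 79%.

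Fifth, the protocol allows up to 250 dyads to be randomised. With 10% lost, 225 remain, and month-6 power with SD 4.12 would be about 80%. That is a permitted maximum; the stated plan is 207.

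Finally, a reader might infer that the larger target contradicts the protocol's aim of detecting the smallest difference that matters clinically. The protocol calls 0.9 to 1.0 days feasible and does not name it as that smallest difference. What is missing is a reason for the change.

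**Conclusion.** The point holds: the recalculated N is wrong as written. The documents disagree on the baseline rate, neither usable reading gives 188 (about 147-154, or 134-141), the Poisson description conflicts with the quoted mean, median and SD, and no timepoint, number of assessments or correlation is attached. The stated 80% is therefore unsupported.

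A reader might go further and conclude that the trial is underpowered. The documents do not show that. For a control mean of 10.25, power at 188 runs from about 69% (dispersion-adjusted count model, month 6) through 72-79% (t-test, month 6) to 88-93% (t-test, two-visit mean, correlation 0.3). The direction depends on the timepoint and on how the spread behaves near 14 days.

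These figures assume 1:1 allocation, 188 evaluable dyads, and that the baseline SD from 60 participants carries over to follow-up, either unchanged in both arms or shrinking with m(14 − m) in the intervention arm. The two-visit figures also assume equal SDs at both visits.

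This should be fixed, because the sample size rests on it and the correction is cheap.

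**What to change.** In both documents:

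1. Retrieve the inputs of the September 2015 calculation, reconcile 0.8 with 10.25, and give the unit and exposure period.
2. Name one primary timepoint and tie the calculation to it. If it is the two-visit mean, state the correlation.
3. Delete the statement that the distribution approximates a Poisson. Restate power at 188 evaluable dyads for the planned two-sample t-test. If the count model is kept, add its power with the observed dispersion. Use an SD in each arm that is possible on a 0-14 scale. If the control mean is 10.25, the values are those in step 6 of the working, with their assumptions stated. If it is 11.2, compute them afresh with a feasible SD.
4. State the implied difference in days (1.54 for 10.25; 1.68 for 11.2) and why it differs from the earlier 0.9 to 1.0.

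The cost is wording and the retrieval of old inputs. The stated power may come out less favourable than 80%. Enrolment and conduct do not change.

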The IMPACT DC Asthma Clinic is a unique program of asthma care, education and care coordination at Children’s National Health System that targets children who are heavily dependent on emergency departments for episodic care, and is designed to transition patients to more effective longitudinal asthma care in their primary medical care homes.

In its pivotal randomized controlled trial, the IMPACT DC intervention improved outcomes in multiple domains (Figures 3a and 3b).³³ Of note, it increased adjusted adherence to ICS by greater than 100% at six month follow-up [adjRR 2.03, 95% confidence intervals (1.57, 2.63)] and reduced the rate of ED visits for asthma by over 40% [adjRR 0.54, 95% confidence intervals (0.40, 0.72)]. The intervention also improved multiple other proximal and distal measures of adherence and health outcomes, including asthma-related quality of life.

| | |
|-----------|-----------|
| Figure 4a | Figure 4b |
|-----------|-----------|

While demonstrating the efficacy of IMPACT DC’s intervention within a clinical trial is impressive, IMPACT DC’s existence has also been associated with a dramatic and sustained 40% drop in the rate of ED visits for asthma among all DC youth with asthma. This drop has occurred at a time when the overall rate of ED visits for all reasons by DC youth has been steadily rising (Figures 4a and 4b).

These improvements in care and outcomes among at-risk DC youth with asthma are impressive, but significant work remains. Even within the context of IMPACT DC’s tightly scripted and guideline-based program of care, adjusted ICS adherence declined to nearly 50% within the intervention group by six months. Similarly, the rate of ED visits for asthma among DC youth in 2009 was still nearly three times the national rate.⁴ ***The guideline-based IMPACT DC intervention, like validated interventions everywhere that target asthma disparities, needs to improve further.***

C.2. Stress Management

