The community wellness coaches that implement the intervention will be selected based on prior experience promoting healthy lifestyle behaviors in community settings, including individuals with experience as a community health worker, a practitioner of complementary and integrative health therapies. They will be employed by Children's National, and will participate training activities and ongoing supervision with our research team staff. Training will be led by Drs. [name] and [name], and topics will include:

- human subjects research, privacy protections, and informed consent,
- socialization with other coaches,
- an overview of this study and the role of coaches,
- coach interaction guidelines (e.g., confidentiality, rapport building, active listening,

- crisis/emergency situations),
- role-playing mentorship skills, and
- an overview of participant assignment, call structure, and supervision

Emphasized throughout the training will be the supportive role of the coach, and the distinction between their role and that of a health care team provider. Coaches will be trained to *not* give any medical advice and to refer participants requesting asthma management information to their medical team. Participants will also be informed of the limitations of the role of their assigned coach.

Supervision will occur on a monthly basis with [name] and/or [name]. This training system worked well with prior studies conducted by [name].

D.10. STATISTICAL ANALYSES

General Considerations

All analyses will be conducted on an intention-to-treat paradigm using all data collected. All analyses will be conducted with two-tailed $\alpha=0.05$ for significance.

To address aim 1: To measure completion of the intervention's components by participants randomized to the intervention. Summary statistics of all variables will be described. For continuous variables, we will calculate the mean, median, standard deviation, minimum and maximum. For categorical variables, we calculate the count and the percentage.

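### The 80% power at N = 188 for a rate ratio of 1.15 does not follow from the plan's stated inputs, and the plan does not show that the ratio is attainable on a 0-14 day scale.

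*Protocol*

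**What the plan says.** Protocol section D.10 (Sample Size Considerations) describes two calculations. The initial one assumes that "the improvements of 0.9-1.0 SFD per 14 days are feasible", with SD 2.7, within-subject correlation 0.3 and two assessments, and arrives at 152. The second, dated September 14, 2015, is "based on the baseline data collected from the first 60 participants": mean 10.25, median 11.5, SD 4.12, described as approximately Poisson. It gives 188 for "80% power at a 0.05 significance level", "to detect a response rate ratio of 1.15 with baseline response rate 0.8". The SAP (Sample Size Calculation) repeats the 188 but words the effect as "to detect a response rate ratio of 1.15 with baseline response rate of 10.25". The Protocol then adds attrition: "with 10% percent attrition rate, we now plan to enroll 207 participants".

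Other relevant statements:
- D.10 (General Considerations): "All analyses will be conducted with two-tailed" alpha of 0.05.
- D.10 (aim 2): the primary comparison is a two-sample t-test on the average of months 3 and 6, with Poisson or negative binomial models as a possible alternative. The SAP places the primary analysis at 6 months.
- D.6: the outcome counts days out of the prior 14.
- D.2: both arms receive clinic care plus three months of care coordination.
- C.1: in its own trial that clinic programme "increased adjusted adherence to ICS by greater than 100% at six month follow-up" and reduced ED visits (adjusted RR 0.54).

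**The concern.** Three things stand out. The two documents attach different rates to the same N. A Poisson variance is assumed for data whose variance exceeds the mean, while the planned test is a t-test. And the rate is a baseline value, whereas the comparison is made after both arms have had clinic care, on a scale that stops at 14.

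At stake is how the result will be read. A null finding would be judged against a claim of 80% power for a 15% gain. If the inputs do not give that power, or the scale leaves little room for that gain, the claim misdescribes what the trial could detect.

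**Working it through.** **Inputs.** Two-sided alpha 0.05 and 80% power, so (1.960 + 0.842)² = 7.849. Ratio 1.15, ln(1.15) = 0.1398. Mean 10.25, SD 4.12, correlation 0.3, N = 188. Allocation is not stated; 1:1 (94 per arm) is assumed. The correlation of 0.3 belongs to the initial calculation and is carried over here.

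**The initial 152 reproduces.** Averaging two visits gives SD 2.7 × √((1 + 0.3)/2) = 2.18. For a difference of 1.0, a two-sample t-test then needs 76 per arm, 152 in total.

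**The revised 188 does not.** Poisson, n per arm = 7.849 × (1/λ + 1/(1.15λ)) / 0.1398²:

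| Reading of the rate | Total N |
|---|---|
| 10.25 per 14 days (SAP) | 2 × 73.3, i.e. 148 |
| 10.25 with overdispersion 4.12²/10.25 = 1.66 | 2 × 121.4, i.e. 244 |
| 0.8 per 14 days | about 1,880 |
| 0.8 per day, 0.8 × 14 = 11.2 | about 134 |

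Other standard Poisson formulas move the 10.25 result only within 147-154. A value near 188 appears only with inputs that neither document states, for example a rate of 0.8 × 10.25 = 8.2 (183-192 depending on the formula), or 11.2 with a covariate R² of 0.25 (187.6).

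**Power at 94 per arm, control mean 10.25, ratio 1.15.** The difference is 0.15 × 10.25 = 1.54 days. For two visits the SD is 4.12 × √0.65 = 3.32.

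| Method | Power, 1.54 days | Power, 1.0 day |
|---|---|---|
| Poisson | 89% | – |
| Poisson, overdispersion 1.66 | 69% | – |
| t-test, one visit, SD 4.12 | 72% | 38% |
| t-test, two-visit average, SD 3.32 | 88% | 54% |

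**Attainability.** The largest control mean compatible with a ratio of 1.15 is 14/1.15 = 12.17. Below it, the share of remaining symptom days that must disappear is 0.15m/(14 − m). The documents give no follow-up control mean m, so a range is assumed:

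| Control mean m | Gain needed (days) | Room left (days) | Share removed |
|---|---|---|---|
| 10.25 | 1.54 | 3.75 | 41% |
| 11 | 1.65 | 3.0 | 55% |
| 11.5 | 1.73 | 2.5 | 69% |
| 12 | 1.80 | 2.0 | 90% |

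**Attrition.** 188 × 1.1 = 206.8, hence 207. But 207 × 0.9 = 186.3, below 188; the correct step is 188/0.9 = 208.9, i.e. 209.

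**The case against.** A reader might infer that the stated power holds only if usual care brings no improvement. The documents do not support that. With the ratio fixed at 1.15, Poisson power rises with the control mean: 88.7% at 10.25, 90.8% at 11, 91.9% at 11.5, 93.0% at 12. The ratio stays possible until controls have improved by 12.17 − 10.25 = 1.92 days. Power falls only under an added assumption that the achievable effect shrinks near the ceiling. For example, hold the cut in symptom days at 41% and use a beta-binomial matched to mean 10.25 and SD 4.12. Power at control means of 10.25 / 11 / 11.5 / 12 is then about 80 / 68 / 59 / 48% with one visit and 93 / 85 / 77 / 66% with two. Both the constant cut and the distribution are outside the plan. Still, the fixed-ratio reading needs a gain that grows from 1.54 to 1.80 days while the room shrinks from 3.75 to 2.0, so it does not show that 1.15 is attainable.

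Improvement under usual care is itself an inference. The text of C.1 reports adherence, ED visits and quality of life, not symptom-free days, and says adherence had declined to nearly 50% by six months. The Protocol's 0.8, if meant per day, is 11.2 days, already above the baseline mean. Neither document says so.

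The 0.9-1.0 day figure belongs to the initial calculation. That is so, but D.10 still presents the trial as aimed at the smallest clinically significant difference and gives no reason for the larger target.

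The attrition shortfall is trivial: two participants, under half a percentage point of power, and the Protocol allows up to 250 to be randomised. Point estimates and 95% CIs are planned, which limits misreading of a null result but does not correct the stated power.

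**Conclusion.** The point holds as an unsupported power statement. The rate differs between the documents (0.8 and 10.25), and 188 follows from neither. At 10.25, power ranges from 69% to 89% depending on variance model and number of visits, so 80% should not be presented as the power at that rate either. The target of 1.54 days exceeds the 0.9-1.0 day called feasible by more than half; for 1.0 day, power is 38% (6-month analysis) or 54% (3- and 6-month average). The plan neither forecasts the follow-up control mean nor discusses the ceiling at 14, so attainability of 1.15 is unjustified rather than disproved, except above 12.17 where it is impossible.

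These figures assume 1:1 allocation, a follow-up SD equal to the baseline 4.12 and, for two visits, a correlation of 0.3. The baseline mean is only approximately pre-treatment, because the interview may fall up to ten days after consent.

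**What to change.** In the sample-size paragraphs of both documents:

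1. Reconcile 0.8 with 10.25, give the unit, and state the formula and all inputs that produced 188.
2. Restate the target as a difference in days, or as a ratio of symptom days (14 minus symptom-free days), and justify it against the 0.9-1.0 day figure.
3. Give power for the planned t-test with SD 4.12, separately for the 6-month analysis and the 3- and 6-month average. Tabulate it over assumed control follow-up means of 10.25 to 12, with the effect and distribution assumptions labelled as such.
4. Correct the attrition step to 209, or state that 207 yields 186 analysed.

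Do not replace the present text with a statement that 80% applies at 10.25. The cost is one rewritten paragraph in each document, with no added enrolment required. The downside is a less favourable stated power.

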The study team has a strong record of retention, and [name] completed studies have had >89% success rates of phone follow-up at six months. The study team will utilize the following procedures developed for prior studies, which have been essential for high retention rates. At enrollment, the research staff will request multiple phone numbers and an email address from each participant, and will also request information on an alternate person that we may contact if we have difficulty reaching them for follow-up. This is necessary due to both the transient nature of our target population, and the fact that phone numbers are frequently disconnected and/or changed. In addition, the study team will maintain a high frequency of contact with all study participants, and regularly request updated contact information. In addition, the study team will engage families at recruitment and emphasize the importance of their ongoing participation. Finally, we will aim to minimize barriers to participation and assure that all research activities are patient- and family-centered.

Participants will receive total compensation of up to \$150 for participation in the study to be dispensed as: \$25 after enrollment and baseline interview, \$35 after the follow-up interview at month 3 and \$40 after the final interview at month 6. In addition, the subset of participants that complete an additional follow-up interview at 12 months will receive \$50 in compensation. Based on previous studies conducted in our research center with similar populations, this amount should be sufficient to compensate participants for their time, but it will not be coercive, minimizing participation solely based on financial gain. Compensation will be provided in the form of gift cards. In addition, we will provide reimbursement for transportation in the form of parking vouchers or metro cards for study-related activities.

D.8. Data Management

All study data will be collected via systems created by the Biostatistics and Study Methodology Division at Children's National, and will comply with all applicable guidelines regarding research participant confidentiality and data integrity.

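### The 10% attrition allowance is multiplied on instead of divided out, so 207 enrolled leaves about 186 evaluable against 188 required; the <5% missing-data figure also needs reconciling with that 10%

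*Protocol*

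**What the plan says.** **Enrolment target.** Protocol D.10 (Sample Size Considerations) reports the recalculation of September 14, 2015: "Based on this distribution, the calculated sample size is 188". It continues: "Therefore, with 10% percent attrition rate, we now plan to enroll 207 participants". The SAP (Sample Size Calculation) carries the same numbers: "Therefore, with 10% percent attrition rate, we planned to enroll 207 participants".

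**Superseded calculation.** D.10 also keeps the initial plan, 152 raised to 168 for 10% attrition, and a table of 21 rows with a column of N inflated for 10% attrition. Both belong to the calculation with a standard deviation of 2.7, which the 2015 recalculation replaced.

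**Ceiling.** D.4 sets a goal of randomising up to 250 dyads.

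**Expected missingness.** D.10 (Missing Data) says: "Based on our prior studies, we anticipate a rate of missing data for the primary outcome of <5" per cent. The sentence before it is about staff filling in every data field. The sentence after it is about keeping dropout low. The paragraph ends with multiple imputation.

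**Past retention.** D.7 reports that the team's "completed studies have had >89% success rates of phone follow-up at six months".

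**The concern.** An attrition rate is a share of those enrolled, so the enrolment needed is the evaluable number divided by one minus that rate. Multiplying by one plus the rate always gives too few. Here the stated target does not deliver the stated requirement at the stated loss, and both documents repeat the figure.

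The second issue is one of definition. Follow-up interviews are done by phone (D.6), and symptom-free days are a 14-day count (D.6), so a family that cannot be reached has no outcome for that interview. If the figure of under 5% covers every missing primary outcome, it does not fit with 10% attrition a few paragraphs later. If it covers only unanswered items in completed interviews, the two are compatible, but total missingness is then stated nowhere. The total matters because D.10 plans sensitivity analyses that bound the treatment effect from below and above, and the width of such bounds is driven by the missing fraction.

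**Working it through.** **Inputs.** Required N = 188, attrition 10%, target 207 (Protocol D.10 and SAP); power 80%, alpha 0.05, two-tailed (D.10); missing primary outcome under 5% (D.10); past six-month follow-up above 89%, so loss below 11% (D.7); ceiling 250 (D.4).

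**1. Reproduce the plan's figure.** N × (1 + d) = 188 × 1.10 = 206.8, rounded up to 207. This matches. All 21 table rows follow the same rule: for example 152 × 1.10 = 167.2, giving 168, and 186 × 1.10 = 204.6, giving 205. In every row, 90% of the inflated number is below that row's N (168 × 0.90 = 151.2, against 152).

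**2. Apply the stated loss.** 207 × 0.90 = 186.3, so about 186 evaluable.

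**3. Correct inflation.** N / (1 − d) = 188 / 0.90 = 208.9, rounded up to 209. Check: 209 × 0.90 = 188.1.

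**4. Effect on power.** Taking 188 as giving exactly 80%, power at n is approximately Φ[(1.96 + 0.842) × √(n/188) − 1.96].

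| Loss from 207 | Evaluable | Power on the plan's own basis |
|---|---|---|
| 5% | 196.7 | above 80% |
| 10% | 186.3 | about 79.6% (n = 186) |
| 11% | 184.2 | about 79.2% (n = 184) |

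At the ceiling, 250 × 0.90 = 225, well above 188.

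**5. The two missingness figures as counts.** 10% of 207 is 20.7, about 21 children. Under 5% of 207 is fewer than 10.35, so at most 10. The count of 21 assumes that a lost child has no usable outcome. D.10 tests the average of the 3- and 6-month values, so a child seen only at month 3 would be partly observed. Under Hypothesis 1 (Specific Aims) and the SAP, which look to 6 months, that child would be missing.

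**6. Why the total matters (illustration).** The documents do not define the highest and lowest treatment effects. My assumptions are: the same missing fraction p in each arm, missing values set to 0 or 14 days, and an observed difference of 1.0 day (the initial design target). Sampling error is ignored. The bounds are then (1 − p) × 1.0 ± 14p.

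- p = 0.05: 0.95 ± 0.70, that is 0.25 to 1.65
- p = 0.10: 0.90 ± 1.40, that is −0.50 to 2.30

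Under these assumptions the interval excludes zero at 5% and includes it at 10%.

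**The case against.** **The gap is trivial.** Two participants in 209 is 1%, and 0.4 points of power changes no decision. This stands, and it sets the severity. It does not make 207 the right figure for 188 at 10% loss.

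**The ceiling of 250 covers it.** Partly. Recruiting beyond 207 is allowed and would close the gap, but 250 is an upper limit and 207 is the planned enrolment named in both documents.

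**188 is itself uncertain, so correcting by two is false precision.** This stands as a caution. The Protocol pairs 188 with a baseline rate of 0.8 ("can achieve 80% power at a 0.05 significance level to detect a response rate ratio of 1.15 with baseline response rate 0.8") and the SAP with 10.25 ("detect a response rate ratio of 1.15 with baseline response rate of 10.25"). Standard two-sided Poisson formulas with equal arms do not return 188. They give about 148–154 in total at 10.25 over one 14-day period, 134–141 at 0.8 per day over 14 days, and about 1,880–1,970 at 0.8 per single unit of exposure. That is a separate and larger matter; here 188 is taken as given.

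**The 21 table rows are not 21 further faults.** Correct. The table and the step from 152 to 168 are superseded, and recomputing them leaves the current target untouched.

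**Under 5% and 10% may measure different things.** This stands. A reader might infer that under 5% cannot hold alongside 10% attrition, but the preceding sentence on data fields supports an item-level reading, and a 10% planning allowance may simply be conservative. A reader might also infer that the retention record contradicts under 5%. It does not: above 89% is a lower bound, consistent with 10% loss and also with less than 5%. Finally, the Protocol anticipates the figure; it does not promise it.

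**Conclusion.** Minor, but wrong as written. At the plan's own 10% attrition, 207 enrolled yields about 186 evaluable, not 188. The cost is about 0.4 points of power (79.6% against 80%), provided that 188 gives exactly 80% and that attrition means a share of those enrolled with no usable outcome. The documents do not support reading this as a materially underpowered trial on account of the dropout step.

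On missingness, the supportable conclusion is that the figures of under 5% and 10% are left unreconciled. The documents neither show that they conflict nor settle which one describes the total.

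**What to change.** 1. In Protocol D.10 and the SAP, do one of two things. Either keep 207 and state that about 186 evaluable participants are expected at 10% attrition (about 79.6% power on the plan's own basis), or state 209 as 188 / 0.90, which lies within the ceiling of 250.
2. For consistency, recompute the table's attrition column as N / 0.90 (for example 152 becomes 169 and 186 becomes 207), or mark the table as superseded. Neither alters the current target.
3. In D.10 (Missing Data), say whether under 5% means item non-response among completed interviews, and give separately the total expected missingness for the primary outcome including dropout. That total is about 10% on the plan's own attrition figure.

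The cost is a few words in two documents. Choosing 209 adds two participants; keeping 207 means printing a power figure slightly below 80%.
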